2.0 TRIAL DESIGN

2.1 Trial Design

This is a double-blind randomized phase III trial of pembrolizumab plus best supportive care (BSC) versus placebo plus BSC in Asian subjects with previously systemically treated advanced hepatocellular carcinoma (HCC). To be eligible, subjects must have documented objective radiographic progression of disease (PD) on or after stopping treatment with sorafenib or oxaliplatin-based chemotherapy, or else be intolerant of sorafenib or oxaliplatinbased chemotherapy as defined in Section 5.1.2. They also must have disease not amenable to a curative treatment approach (e.g., transplant, surgery, or ablation). In order to be eligible, subjects must have at least one measurable lesion that is confirmed by the investigator per Response Evaluation Criteria in Solid Tumors (RECIST) 1.1 prior to randomization. Subjects will be enrolled regardless of tissue programmed death ligand 1 (PD-L1) biomarker status. Subjects will not be required to provide a tumor tissue sample for biomarker analysis, but are strongly urged to do so if tissue is available. Available samples will be evaluated at a central laboratory for expression status of PD-L1 by immunohistochemistry (IHC). Approximately 450 subjects will be randomized at a 2:1 ratio to receive pembrolizumab 200 mg intravenously (IV) every 3 weeks (Q3W) or placebo (IV administration of saline) Q3W. Subjects from both arms can receive BSC as per local standard of care.

The primary objective of this trial is to compare the overall survival (OS) in subjects who receive pembrolizumab plus BSC and those who receive placebo plus BSC. On-study imaging assessments will be performed Q6W calculated from the date of randomization and independent of treatment delays. RECIST 1.1 will be used by the site for treatment decisions until the first radiologic evidence of progressive disease (PD).

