The multi-targeted tyrosine kinase inhibitor sorafenib is the current standard of care worldwide for the treatment of patients with advanced HCC and preserved liver function based on a large Phase III trial in a Western population. In this trial, TTP was 5.5 months, and OS was 10.7 months in the treatment arm, compared with 2.8 and 7.9 months in the control arm respectively [8]. A similar study conducted in the Asia-Pacific region showed an almost identical hazard ratio for sorafenib of 0.68 [95% CI 0.50-0.93], p=0.014, although overall survival was shorter in this trial (6.5months vs. 4.2 months) [9]. In parts of Asia, the FOLFOX regimen (folinic acid, 5-fluorouracil, and oxaliplatin) has also been approved, based on a randomized trial comparing FOLFOX with doxorubicin [10]. In this trial, there was a non-significant trend toward improved OS in the FOLFOX arm (6.4 months vs. 4.97 months, HR of 0.8 [95% CI 0.63-1.02]), but in a pre-specified Chinese substudy, the FOLFOX arm was superior to doxorubicin (5.7 months vs. 4.3 months, HR of 0.74 [95% CI 0.55-0.98]; p=0.03) [11]. Based on comparable survival data with sorafenib, the FOLFOX regimen is recommended for 1st line treatment of advanced HCC by China liver cancer guidelines [12]. In Thailand, oxaliplatin was also approved for advanced HCC in 2014. Oxaliplatin-based regimens are also included in the Korea Practice Guideline for the

Protocol/Amendment No.: 394-06

management of HCC [13]. Despite these advances, continued investigation of additional agents for advanced HCC patients remains crucial.

In the second-line setting, there is no approved agent for treatment of advanced HCC in China and other Asian regions. Several large randomized trials failed to show a significant survival advantage of various agents against placebo in the second line, including brivanib [14], everolimus [15] and ramucirumab [16]. Smaller studies have suggested the possible efficacy for MET inhibitors and regorafenib in advanced HCC [17][18]. Chemotherapy drugs including capecitabine and the gemcitabine/oxaliplatin (GEMOX) combination have also been used in the second line in small trials [19][20]. However, there are no agents or combinations yet approved for second-line HCC, underscoring the high unmet medical need for this disease. The standard of care for second-line treatment for advanced HCC is still best supportive care in Asian countries

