5.0 METHODOLOGY

5.1 **Entry Criteria**

Diagnosis/Condition for Entry into the Trial

Male/Female Asian subjects with advanced HCC after progression on or intolerance to sorafenib or oxaliplatin-based chemotherapy with no curative option will be enrolled in this trial.

5.1.2 **Subject Inclusion Criteria**

In order to be eligible for participation in this trial, the subject must:

1. Be willing and able to provide written informed consent for the trial. The subject may also provide consent for Future Biomedical Research (FBR). However, the subject may participate in the main trial without participating in FBR.

03-Nov-2022 Confidential

085/RXM

Protocol/Amendment No.: 394-06

2. Be ≥ 18 years of age on day of signing informed consent.

3. Have a HCC diagnosis confirmed by radiology, histology, or cytology (fibrolamellar, and mixed hepatocellular/cholangiocarcinoma subtypes are not eligible).

Note: Radiologic confirmation diagnosis is provided by the study site. Definition of radiological confirmation: Clinical findings consistent with the diagnosis of liver cirrhosis and a liver mass measuring at least 2 cm with characteristic vascularization (intense enhancement seen in the hepatic arterial-dominant phase and contrast washout in the late portal venous phase) seen in either triphasic computed tomography (CT) scan or magnetic resonance imaging (MRI).

- 4. Have Barcelona Clinic Liver Cancer (BCLC) Stage C diseases or BCLC Stage B disease not amenable to locoregional therapy or refractory to locoregional therapy and not amenable to a curative treatment approach (see Appendix 12.8).
- 5. Have a Child-Pugh A liver score within 7 days prior to first dose of study drug.
- 6. Have a predicted life expectancy of >3 months.
- 7. Have at least one measurable lesion based on RECIST 1.1 as determined by investigator. Target lesions situated in a previously irradiated or post locoregional treatment area are considered measurable if progression has been demonstrated in such lesions

Note: the same image acquisition and processing parameters should be used throughout the study for a given subject.

- 8. Have a performance status of 0 or 1 using the Eastern Cooperative Oncology Group (ECOG) Performance Scale within 7 days of first dose of study drug.
- 9. Have documented objective radiographic progression during or after treatment with sorafenib or oxaliplatin-based chemotherapy, or intolerance to sorafenib or oxaliplatin-based chemotherapy.

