 - Note: (1) Sorafenib intolerance definition: Any Grade ≥2 drug-related AE which, despite supportive therapy, recurred after a sorafenib treatment interruption of at least 7 days and dose reduction resulting in the subject requesting, or the physician recommending discontinuation of medication due to toxicity.
 - (2) Oxaliplatin-based chemotherapy intolerance definition: 1) having had at least one dose of chemotherapy and 2) having a Grade ≥2 drug-related AE which both a) persisted in spite of comprehensive supportive therapy according to institutional standards and b) persisted or recurred after dose reduction and resulted in the subject requesting or the physician recommending discontinuation of medication due to the toxicity

Protocol/Amendment No.: 394-06

10. Female subjects of childbearing potential must have a negative urine or serum pregnancy test within 72 hours prior to receiving the first dose of study medication (Cycle 1, Day 1). If the urine test is positive or cannot be confirmed as negative, a serum pregnancy test will be required.

11. Female subjects of childbearing potential (Section 5.7.2) must be willing to use an adequate method of contraception as outlined in Section 5.7.2 – Contraception for the course of the study, starting with the first dose of study medication through at least 120 days or longer based on local regulation after the last dose of study medication.

Note: Abstinence is acceptable if this is the usual lifestyle and preferred contraception for the subject.

12. Male subject of childbearing potential (Section 5.7.2) must agree to use an adequate method of contraception as outlined in Section 5.7.2 - Contraception, starting with the first dose of study medication (Cycle 1, Day 1) through 120 days after the last dose of study medication

Note: Abstinence is acceptable if this is the usual lifestyle and preferred contraception for the subject.

13. Demonstrate adequate organ function as defined in Table 1. All screening laboratory tests should be performed within 7 days prior to first dose of study drug.

Table 1 Adequate Organ Function Laboratory Values

System	Laboratory Value				
Hematological	-				
Absolute neutrophil count (ANC)	≥1200/µL				
Platelets	≥60,000/µL				
Hemoglobin	≥8 g/dL without transfusion or EPO dependency within 7				
Hemogloom	days.				
Renal					
Creatinine OR	≤1.5×ULN OR				
Measured or calculated creatinine clearance	\geq 60 mL/min for subject with creatinine levels >1.5 ×				

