5.1.3 Subject Exclusion Criteria

The subject must be excluded from participating in the trial if the subject:

- 1. Is currently participating, or has participated in any study of an investigational agent and received its study therapy, or used an investigation device within 4 weeks prior to the first dose of our study treatment. Has received herbal/complementary oral or IV medicine used as systemic anti-cancer therapy within 2 weeks prior to the first dose of our study treatment. Subjects must also have recovered from associated therapy (i.e., to Grade ≤1 or baseline) and from adverse events due to any prior therapy.
- 2. Has received sorafenib or oxaliplatin-based chemotherapy within 14 days of first dose of study medication, or received more than one systemic anticancer drug in the advanced hepatocellular cancer setting.
- 3. Has had esophageal or gastric variceal bleeding within the last 6 months.
- 4. Has clinically apparent ascites on physical examination.

Note: ascites detectable on imaging studies only IS allowed.

- 5. Portal vein invasion at the main portal branch (Vp4), inferior vena cava, or cardiac involvement of HCC based on imaging.
- 6. Has had clinically diagnosed hepatic encephalopathy in the last 6 months. Subjects on rifaximin or lactulose to control their encephalopathy are not allowed.
- 7. Has had a solid organ or hematologic transplant.
- 8. Had prior systemic therapy for HCC in the advanced (incurable) setting other than sorafenib or oxaliplatin-based chemotherapy, prior to start study drug.
- 9. Has a known severe hypersensitivity (≥ Grade 3) to pembrolizumab, its active substance and/or any of its excipients. (Refer to the respective Investigator's Brochure for a list of excipients.)
- 10. Has active autoimmune disease that has required systemic treatment in past 2 years (i.e., with use of disease-modifying agents, corticosteroids, or immunosuppressive drugs). Replacement therapy (e.g., thyroxine, insulin, or physiologic corticosteroid replacement therapy for adrenal or pituitary insufficiency, etc.) is not considered a form of systemic treatment.

Protocol/Amendment No.: 394-06

11. Has a diagnosis of immunodeficiency or is receiving systemic steroid therapy or any other form of immunosuppressive therapy within 7 days prior to the first dose of trial treatment. The use of physiologic doses of corticosteroids may be approved after consultation with the Sponsor.

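### Does the one-drug limit in Exclusion 2 bar the FOLFOX-treated subjects whom the rest of the protocol admits?

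*Protocol*

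**What the plan says.** Exclusion 2 in Protocol 5.1.3 has two limbs. The first is a washout: "Has received sorafenib or oxaliplatin-based chemotherapy within 14 days of first dose of study medication". The second is a cap on earlier treatment: "or received more than one systemic anticancer drug in the advanced hepatocellular cancer setting". The unit of the cap is the drug, and no section says how a combination is to be counted.

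Elsewhere oxaliplatin-based chemotherapy is an accepted history:

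- Protocol 2.1 describes eligible subjects as progressing "on or after stopping treatment with sorafenib or oxaliplatin-based chemotherapy", or as intolerant of either.
- Inclusion 9 (Protocol 5.1.2) reads "Have documented objective radiographic progression during or after treatment with sorafenib or oxaliplatin-based chemotherapy", with intolerance as the alternative. Its note (2) defines chemotherapy intolerance, starting from "having had at least one dose of chemotherapy".
- Exclusion 8 removes subjects who "Had prior systemic therapy for HCC in the advanced (incurable) setting other than sorafenib or oxaliplatin-based chemotherapy", which exempts those two treatments by name.
- Protocol 5.4 stratifies randomisation by prior sorafenib versus prior chemotherapy.

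On FOLFOX itself, Protocol 4.1 says that in parts of Asia "the FOLFOX regimen (folinic acid, 5-fluorouracil, and oxaliplatin) has also been approved", and that "the FOLFOX regimen is recommended for 1st line treatment of advanced HCC by China liver cancer guidelines".

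**The concern.** FOLFOX is the only first-line oxaliplatin combination that the documents name, and the trial enrols Asian subjects only. If each component is counted, a FOLFOX-treated subject satisfies Inclusion 9 and passes Exclusion 8 but fails Exclusion 2. Only a single-agent oxaliplatin history would then meet every criterion as written.

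Three things could be at stake. Sites might screen inconsistently. Two monitors might classify the same randomised subject differently, one as eligible and one as an eligibility deviation. If the literal rule had been enforced, it would also have narrowed the chemotherapy level of the randomisation factor, and with it the prior-treatment subgroup planned for overall survival in Protocol 8.10 and SAP 3.9.

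**Working it through.** The plan gives no figure on this point, so there is nothing to reproduce. The check is a count against the limit of 1 under each possible unit, followed by a reading of the context.

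**Count by unit.** Components are taken from Protocol 4.1. FOLFOX is 5-fluorouracil + oxaliplatin = 2 drugs, or 2 + 1 = 3 if folinic acid is counted; the documents do not call folinic acid an anticancer drug. Sorafenib adds 1.

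| Prior history | Drugs | Regimens | Lines | Result |
|---|---|---|---|---|
| Sorafenib alone | 1 | 1 | 1 | passes under every unit |
| Oxaliplatin alone | 1 | 1 | 1 | passes under every unit |
| FOLFOX alone | 2 to 3 | 1 | 1 | fails by drug only |
| Sorafenib, then FOLFOX | 3 to 4 | 2 | 2 | fails under every unit |
| Sorafenib with FOLFOX together | 3 to 4 | 1 or 2 | 1 | depends on the unit |

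Sequential use is therefore not ambiguous. The last row is hypothetical, because the documents describe no such history. The only practical case that turns on the unit is FOLFOX alone.

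**Which reading the context supports.**

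1. The washout limb of Exclusion 2 sets sorafenib and oxaliplatin-based chemotherapy side by side as equivalent items. A washout for chemotherapy makes sense only if chemotherapy-treated subjects may enter.
2. Exclusion 8 exempts that chemotherapy by name, Inclusion 9 makes it a qualifying history, and Protocol 5.4 gives it a randomisation level.
3. The title in Protocol 1.0 and the design overview in Table 8 call the trial second-line, which points to counting lines.
4. Protocol 12.10 lists FOLFOX as a regimen. Protocol 4.1 also groups the gemcitabine/oxaliplatin combination under chemotherapy drugs, so the protocol uses the noun loosely elsewhere.

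The literal reading would defeat most of what these provisions admit. By regimen or by line, FOLFOX alone counts as 1 and all the criteria agree.

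**What depends on the wording.**

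- *Primary analysis.* Protocol 8.5.1 keeps every randomised subject in the group assigned. The strata in Protocol 8.6.1.1 and SAP 3.5.1 are macrovascular invasion, alpha-fetoprotein and region, and prior treatment is not among them. The survival test, its alpha, its power and its strata are untouched.
- *Subgroup.* Prior treatment is a planned survival subgroup, so its make-up would have changed had sites applied the literal rule. Nothing in the documents indicates that they did.
- *Future screening.* SAP section 2 states that all subjects in the intention-to-treat population had at least 24 weeks between randomisation and the data cutoff for the second interim analysis. Recruitment therefore appears to be over.
- *Deviation listings.* No analysis in either document uses eligibility-deviation status.

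**The case for a change.** The strongest argument for a change is that exclusion criteria are applied at many sites and audited as written. Knowing that a component count is not meant does not tell a site whether to count regimens or lines, and those two can differ for concurrent sorafenib and FOLFOX. One clarifying sentence would be cheap. The text may also not be purely historical, since Protocol 2.1 makes second-course treatment conditional on still meeting the entry criteria.

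Part of this stands. The wording is loose, and no section resolves it expressly. The rest carries little weight. Regimen and line give the same answer for FOLFOX alone and for sequential therapy, and they can part only on a history that the documents never describe. The detailed retreatment conditions in Protocol 7.1.6.2 do not repeat the cap on earlier drugs, and a subject admitted on the sensible reading would be judged by the same reading again. A sentence added now would come after recruitment and would serve only a classification that feeds no described analysis.

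**Conclusion.** The literal mismatch is genuine: at least 2 drugs against a limit of 1 for FOLFOX. It is a slip of wording that the surrounding criteria correct. No change to the plan follows, because sites would fill the gap sensibly and an amendment at this stage would gain nothing that an analysis uses.

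The conclusion rests on two assumptions. The first is that sites read Exclusion 2 together with Inclusion 9 and Exclusion 8; the documents neither show nor suggest otherwise. The second is that enrolment is complete, as the SAP's statement on 24-week follow-up implies. The number of subjects affected is unknown: neither document gives the share with prior chemotherapy or the split between single-agent and combination use. If it emerged that some sites had enforced the literal count, the effect would fall on the composition of the chemotherapy subgroup. The validity of the randomised comparison would not be affected.

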5.2 Trial Treatment(s)

Study treatment to be used in this trial is outlined below in Table 2. BSC will vary with local treatment practices.

Protocol/Amendment No.: 394-06

Table 2 Trial Treatment

Drug	Dose/Potency	Dose Frequency	Route of Administration	Regimen	Use
Pembrolizumab (MK-3475)	200 mg	Q3W	IV infusion	IV infusion	Experimental
Placebo	0.90% w/v NaCI	Q3W	IV infusion	IV infusion	Control

Trial Treatment should begin within 3 days of randomization. However, every effort should be made to begin trial treatment on the day of randomization.

All supplies indicated in Table 2 above will be provided centrally by the Sponsor or locally by the trial site, subsidiary or designee, depending on local country operational or regulatory requirements.

For any commercially available product that is provided by the trial site, subsidiary or designee every attempt will be made to source these supplies from a single lot/batch number. The trial site is responsible for recording the lot number, manufacturer, and expiry date for any locally purchased product as per local guidelines unless otherwise instructed by the Sponsor.

The investigator shall take responsibility for and shall take all steps to maintain appropriate records and ensure appropriate supply, storage, handling, distribution and usage of trial treatments in accordance with the protocol and any applicable laws and regulations.

5.2.1 Dose Selection/Modification

5.2.1.1 Dose Selection (Preparation)

The rationale for selection of the dose of pembrolizumab to be used in this trial is provided in Section 4.0, Background and Rationale. Details on preparation and administration of study drug are provided in the Pharmacy Manual.

Administration of BSC should follow local treatment guidelines.

Protocol/Amendment No.: 394-06

5.2.1.2 Dose Modification (Escalation/Titration/Other)

5.2.1.2.1 Immune-Related Events and Dose Modification (Withhold, Treat, Discontinue)

Dose Modification and Toxicity Management for Non-hepatic Immune-related AEs Associated with Pembrolizumab

AEs associated with pembrolizumab exposure may represent an immune-related response. These irAEs may occur shortly after the first dose or several months after the last dose of pembrolizumab treatment and may affect more than one body system simultaneously. Therefore, early recognition and initiation of treatment is critical to reduce complications. Based on existing clinical study data, most irAEs were reversible and could be managed with interruptions of pembrolizumab, administration of corticosteroids and/or other supportive care. For suspected irAEs, ensure adequate evaluation to confirm etiology or exclude other causes. Additional procedures or tests such as bronchoscopy, endoscopy, skin biopsy may be included as part of the evaluation. Based on the severity of irAEs, withhold or permanently discontinue pembrolizumab and administer corticosteroids.

Dose Modification and Toxicity Management Guidelines for Non-hepatic irAEs associated with pembrolizumab monotherapy, coformulations, or IO combinations are provided in Table 3.

Protocol/Amendment No.: 394-06

Table 3 Dose Modification and Toxicity Management Guidelines for Non-hepatic Immune-related Adverse Events Associated with Pembrolizumab Monotherapy, Coformulations or IO Combinations

General instructions:

- 1. Severe and life-threatening irAEs should be treated with IV corticosteroids followed by oral steroids. Other immunosuppressive treatment should begin if the irAEs are not controlled by corticosteroids.
- 2. Pembrolizumab monotherapy, coformulations or IO combinations must be permanently discontinued if the irAE does not resolve or the corticosteroid dose is not ≤10 mg/day within 12 weeks of the last treatment.
- 3. The corticosteroid taper should begin when the irAE is \leq Grade 1 and continue at least 4 weeks.
- 4. If pembrolizumab monotherapy, coformulations or IO combinations have been withheld, treatment may resume after the irAE decreased to ≤ Grade 1 after corticosteroid taper.

irAEs	Toxicity Grade (CTCAEv4.0)	Action With Pembrolizumab Monotherapy, Coformulations or IO Combinations	Corticosteroid and/or Other Therapies	Monitoring and Follow-up

Nephritis and renal dysfunction	Grade 2	Withhold		lminister corticosteroids rednisone 1-2 mg/kg or	•	Monitor changes of renal function
Grade 3 or 4 Perman		Permanently discontinue	equivalent) followed by taper			

Protocol/Amendment No.: 394-06

irAEs	Toxicity Grade (CTCAEv4.0)	Action With Pembrolizumab Monotherapy, Coformulations or IO Combinations	Corticosteroid and/or Other Therapies	Monitoring and Follow-up
Myocarditis	Grade 1	Withhold	Based on severity of AE administer corticosteroids	Ensure adequate evaluation to confirm etiology and/or exclude other causes
	Grade 2, 3 or 4	Permanently discontinue		
All Other irAEs	Persistent Grade 2	Withhold	Based on severity of AE administer corticosteroids	Ensure adequate evaluation to confirm etiology or exclude other causes
	Grade 3	Withhold or discontinue b		
	Recurrent Grade 3 or Grade 4	Permanently discontinue		

AE(s)=adverse event(s); CTCAE=Common Terminology Criteria for Adverse Events; DRESS=Drug Rash with Eosinophilia and Systemic Symptom; GI=gastrointestinal; IO=immuno-oncology; ir=immune related; IV=intravenous; SJS=Stevens-Johnson Syndrome; T1DM=type 1 diabetes mellitus; TEN=Toxic Epidermal Necrolysis; ULN=upper limit of normal.

Note: Non-irAE will be managed as appropriate, following clinical practice recommendations.

^a The decision to withhold or permanently discontinue pembrolizumab monotherapy, coformulations or IO combinations is at the discretion of the investigator or treating physician. If control achieved or ≤ Grade 2, pembrolizumab monotherapy, coformulations or IO combinations may be resumed.

b Events that require discontinuation include, but are not limited to: Guillain-Barre Syndrome, encephalitis, myelitis, DRESS, SJS, TEN and other clinically important irAEs (eg, vasculitis and sclerosing cholangitis).

41

Product: MK-3475

Protocol/Amendment No.: 394-06

Dose modification and toxicity management of infusion-reactions related to pembrolizumab

Pembrolizumab may cause severe or life threatening infusion-reactions including severe hypersensitivity or anaphylaxis. Signs and symptoms usually develop during or shortly after drug infusion and generally resolve completely within 24 hours of completion of infusion. Dose modification and toxicity management guidelines on pembrolizumab associated infusion reaction are provided in Table 4.

Table 4 Pembrolizumab Infusion Reaction Dose modification and Treatment Guidelines

NCI CTCAE Grade	Treatment	Premedication at Subsequent Dosing
Grade 1	Increase monitoring of vital signs as medically	None
Mild reaction; infusion	indicated until the subject is deemed medically	
interruption not	stable in the opinion of the investigator.	
indicated; intervention		
not indicated	G. Y. B. A.	
Grade 2	Stop Infusion.	Subject may be premedicated
Requires therapy or	Additional appropriate medical therapy may	1.5h (± 30 minutes) prior to
infusion interruption but	include but is not limited to:	infusion of study treatment
responds promptly to	IV fluids	with:
symptomatic treatment	Antihistamines	Diphenhydramine 50 mg po
(e.g., antihistamines,	NSAIDs	(or equivalent dose of
NSAIDs, narcotics, IV	Acetaminophen	antihistamine).
fluids); prophylactic	Narcotics	Acetaminophen 500-1000 mg
medications indicated	Increase monitoring of vital signs as medically	po (or equivalent dose of
for ≤24 hrs	indicated until the subject is deemed medically	analgesic).
	stable in the opinion of the investigator.	
	If symptoms resolve within 1 hour of stopping	
	drug infusion, the infusion may be restarted at	
	50% of the original infusion rate (e.g. from 100	
	mL/hr to 50 mL/hr). Otherwise dosing will be	
	held until symptoms resolve and the subject	
	should be premedicated for the next scheduled	
	dose.	
	Subjects who develop Grade 2 toxicity despite	
	adequate premedication should be permanently	
	discontinued from further study drug treatment	

Product: MK-3475 42

Protocol/Amendment No.: 394-06

NCI CTCAE Grade	Treatment	Premedication at Subsequent Dosing
Grades 3 or 4	Stop Infusion.	No subsequent dosing
Grade 3:	Additional appropriate medical therapy may	
Prolonged (i.e., not	include but is not limited to:	
rapidly responsive to	Epinephrine**	
symptomatic medication	IV fluids	
and/or brief interruption	Antihistamines	
of infusion); recurrence	NSAIDs	
of symptoms following	Acetaminophen	
initial improvement;	Narcotics	
hospitalization indicated	Oxygen	
for other clinical	Pressors	
sequelae (e.g., renal	Corticosteroids	
impairment, pulmonary	Increase monitoring of vital signs as medically	
infiltrates)	indicated until the subject is deemed medically	
Grade 4:	stable in the opinion of the investigator.	
Life-threatening;	Hospitalization may be indicated.	
pressor or ventilatory	**In cases of anaphylaxis, epinephrine should	
support indicated	be used immediately.	
	Subject is permanently discontinued from	
	further study drug treatment.	

Appropriate resuscitation equipment should be available at the bedside and a physician readily available during the period of drug administration.

For further information, please refer to the Common Terminology Criteria for Adverse Events v4.0 (CTCAE) at http://ctep.cancer.gov

Other allowed dose interruption for pembrolizumab

Pembrolizumab may be interrupted for situations other than treatment-related AEs such as medical / surgical events or logistical reasons not related to study therapy. Subjects should be placed back on study therapy within 3 weeks of the scheduled interruption, unless otherwise discussed with the Sponsor. The reason for interruption should be documented in the patient's study record.

